8.3 Interim analyses

CCI

CCI

8.4 End of study

End of study occurs when all of the following criteria have been satisfied:

1. The overall study ends when the last patient completes the last study-related phone-call or visit, withdraws from the study or is lost to follow-up.
2. The trial is mature for the analysis of the primary/dual-primary endpoints as defined in the protocol
3. The database has been fully cleaned and frozen for this analysis

9 Trial Governance and Oversight

9.1 Scientific Advisory Committee

This trial was developed in collaboration with a Scientific Advisory Committee (SAC). The SAC comprises the scientific experts from EORTC/ETOP as well as the sponsor (MSD) who provide input with respect to trial design, interpretation of trial results and subsequent peer-reviewed scientific publications.

9.2 Trial Steering Committee

This trial will be conducted in consultation with a Trial Steering Committee. The Trial Steering Committee will be chaired by study coordinators from EORTC and ETOP and comprises:

- ◆ Study Coordinators from each participating group
- ◆ Representative persons from the coordinating group
- ◆ Sponsor personnels
- ◆ Representative of investigators participating in the trial
- ◆ Consulting therapeutic-area experts and clinical trialists

The Trial Steering Committee will provide guidance on the operational aspects of the trial, evaluate recommendations from the Data Monitoring Committee (DMC) and make recommendations to the Executive Oversight Committee (EOC).

Specific details regarding responsibilities and governance of the Trial Steering Committee will be described in a separate charter.

9.3 Executive Oversight Committee

The Executive Oversight Committee (EOC) comprises members of Sponsor Senior Management. The EOC will receive any recommendations made by the Data Monitoring Committee (DMC) and decide upon consultation with the EORTC/ETOP leadership team and the trial steering Committee regarding the trial.

9.4 Data Monitoring Committee

An independent data monitoring committee will be established following EORTC POL-004 “Independent Data Monitoring Committees for EORTC studies” (EORTC IDMC) to provide independent review and assessment of the efficacy and safety data in a systematic manner and to safeguard the interest and safety of the participating patients in the study. Besides its Chair, the EORTC IDMC has a minimum of four (4) permanent members representing each of the following disciplines: medical oncology, radiation oncology, surgical oncology and clinical biostatistics. For interim reviews involving the review of efficacy trial data, the EORTC IDMC will be comprised of all permanent IDMC members and a minimum of three (3) trial specific external members to review the Interim Analysis Report. For interim reviews of safety data only, the EORTC IDMC Chair and at least one of the permanent IDMC members along with a minimum of two (2) trial specific external members will be part of the IDMC.

The IDMC is tasked with making a recommendation to the Sponsor based on their assessment of efficacy and safety information to continue or stop the trial.

No efficacy results will be presented at EORTC Group meetings or elsewhere before the trial is closed to recruitment and the data are mature for the analysis of the primary endpoint, unless recommended otherwise by the EORTC IDMC (Independent Data Monitoring Committee) and approved by EOC.

The membership, key responsibilities of the IDMC, and the corresponding procedures will be defined in an IDMC charter in light of EORTC POL-004.

Safety data are reviewed within the EORTC Headquarters on a regular basis as part of the Medical Review process. Problems which are identified will be discussed with the Study Coordinators and the Sponsor who will take appropriate measures.

Safety information will be reported to the IDMC, approximately every 6 months unless otherwise agreed upon with the IDMC. Unblinding for global safety reasons and unblinding at interim analysis will be performed according to EORTC SOP CM-011-SOP “Blind Studies”. The unblinded Statistician, an independent Statistician at the EORTC Headquarters not involved in the conduct of the trial and the Pharmacovigilance Physician will write the unblinded interim/safety report and will present it to the IDMC.

10 Quality of life assessment

10.1 Rationale

Health related quality of life (HRQoL) is a multidimensional construct, which can be defined as a state of general well being reflecting physical, psychological, and social well being and the impact of the disease and/or treatment related symptoms on daily-life functioning. The patient's subjective perspective is an inherent component of HRQoL and is therefore best assessed via self-administration.

Reducing mortality and morbidity is still the most important factor in cancer clinical research. Nevertheless, issues such as reducing side effects, symptom relief and improving patients' satisfaction have also become relevant parameters in the evaluation of medical strategies. Cancer treatments may produce adverse effects and diminish a patient's quality of life even when survival is extended. Progress in the acceptance of new cancer therapies is sometimes critically dependent on their HRQoL consequences.

10.2 Objective

In the present study, HRQoL is a pre-specified exploratory endpoint. The working hypothesis is that pembrolizumab will result in improved DFS compared to placebo with no significant decrement in HRQoL. It is expected that overall self-reported quality of life should be improved due to the improved tumor control but may be affected by immunotherapy related side-effects (fatigue, nausea, pruritus, diarrhea and rash). In addition, the impact of self-reported common symptoms are of interest.

Therefore, overall HRQoL rating and selected symptoms (pain, fatigue, appetite loss, cough, chest pain and dyspnea) will be of interest for the duration of the treatment and for a limited follow-up period afterwards.

10.3 HRQoL instruments

Health related quality of life will be assessed with the EORTC Quality of Life Questionnaire (QLQ-C30) version 3. This instrument is composed of multi-item and single-item scales. These include five functional scales (physical, role, emotional, social, and cognitive), three symptom (fatigue, nausea and vomiting and pain) and a global health status/QoL scale and six single items (dyspnea, insomnia, appetite loss, constipation, diarrhea and financial difficulties). All scales and single items meet the standards for reliability. The reliability and validity of the questionnaire is highly consistent across different language-cultural groups [Ref. 76]. The average time to complete the questionnaire is approximately 10 minutes.

Additionally, the QLQ-LC13 lung cancer module to the QLQ-C30, which measures HRQoL relevant to specific symptoms (chest pain, cough and dyspnea) common in lung cancer will be included [Ref. 77]. The lung cancer module is meant for use among a wide range of lung cancer patients varying in disease stage and treatment modality. The module comprises 13 questions assessing lung cancer-associated symptoms (cough, haemoptysis, dyspnoea and site specific pain), treatment-related side effects (sore mouth, dysphagia, peripheral neuropathy and alopecia) and pain medication. The EORTC QLQ-C30 version 3 has been translated in over 50 languages according to a standardized translation procedure.

The domains of interest as specified in the previous paragraph are covered by the global health/QoL scale and the pain, fatigue appetite loss, shortness of breath, symptom scales of the QLQ-C30; and the cough, chest pain and dyspnea symptom scales of the QLQ-LC13.

EuroQol (EQ)-5D was developed to assess health outcomes from a wide variety of interventions on a common scale, for purposes of evaluation, allocation and monitoring [Ref. 78]. Index-based values ('utilities') facilitate the calculation of quality-adjusted life years (QALYs) that are used to inform economic evaluations of health care interventions. The EQ-5D-3L descriptive system comprises 5 dimensions: mobility, self-care, usual activities, pain/discomfort and anxiety/depression; each dimension has 3 levels: no problems, some problems, extreme problems. There are more than 100 official language versions of EQ-5D-3L.

English version of these HRQoL Instruments are included as protocol [Appendix E](#), with the list of validated versions available in other languages.

10.4 Study design

HRQoL questionnaires must be filled out at the hospital when patients come for a scheduled visit according to the EORTC "Guidelines for administration of questionnaires" (see [Appendix E](#)). The pre-treatment questionnaires must be filled in within 12 weeks before randomization. Subsequent questionnaires are filled in every 12 weeks, during the 1st year after randomization; every 6 months during the 2nd year and then yearly until year 5. HRQoL data must be collected regardless of the patient's progression status; no further collection is required beyond the fifth year.

The assessment schedule is chosen to coincide as much as possible with the disease assessment schedule in order to maximize compliance. The week 74 assessment therefore corresponds to the last scheduled on-treatment disease assessment visit at week 48 plus 26 weeks (= 6 months). Subsequent assessments occur at 26 weeks (= 6 months) intervals. Collection beyond year 5 is not deemed necessary as most symptoms will have stabilized by then and the available patient population will have decreased due to attrition.

Master copies of the HRQoL questionnaires will be sent to the institutions. Additional copies or translations can be provided upon request via the EORTC contact person. The clinical report forms will include a question whether the HRQoL forms have been filled in, and if not, the reason why. The questionnaire will be handed out to the patients by the investigator or a study nurse prior to seeing the doctor for clinical evaluations. The patient should complete the questionnaires by her/himself in her/his own language during the visit to the outpatient clinic as completely and accurately as possible. In the event telephone transcript is utilized, the designated study staff should capture the patient's responses on the HRQoL forms. It is recommended that a key person (e.g. research nurse) at each center should be responsible for questionnaire data collection in order to optimize the compliance of the patient and to ensure the completeness of the data.

During the study, compliance with completing questionnaires will be investigated at each time point and reviewed twice a year.

10.4.1 HRQoL schedule

The time windows for eligible HRQoL including EQ-5D assessments will be as follows:

Assessment	Time window
Baseline	Can be completed before or on the day of randomization itself but no earlier than 12 weeks before.
Week 12	Can be completed at week 12 (+/-3 weeks) after randomization.
Week 24	Can be completed at week 24 (+/-3 weeks) after randomization.
Week 36	Can be completed at week 36 (+/-3 weeks) after randomization.
Week 48	Can be completed at week 48 (+/-3 weeks) after randomization.
Week 74	Can be completed at week 74 (+/-4 weeks) after randomization.
Week 100	Can be completed at week 100 (+/-4 weeks) after randomization.
Week 152	Can be completed at week 152 (+/-4 weeks) after randomization.
Week 204	Can be completed at week 204 (+/-4 weeks) after randomization.
Week 256	Can be completed at week 256 (+/-4 weeks) after randomization.

 HRQoL data must be collected regardless of the patient's progression status.

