6.7.2 Follow-up in the absence of disease recurrence

The reference date for scheduling follow up visits is day 1 of infusion 1

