6.7.3 Follow-up after disease recurrence

The reference date for scheduling follow up visits is day 1 of infusion 1

For each follow-up visit, the following tests/exams/questionnaires will be collected/performed:

- ◆ HRQoL evaluation : EORTC QLQ-C30 version 3, EORTC QLQ-LC13 and EQ5D.

Note: questionnaires are filled in every 12 weeks (+/- 3 weeks), during the 1st year after randomization; every 6 months (+/- 4 weeks) during the 2nd year and then yearly (+/- 4 weeks) until year 5. **HRQoL data must be collected regardless of the patient's progression status; no further collection is required beyond the fifth year.**

- ◆ Thyroid function: tests are performed every 12 weeks (+/- 2 weeks) for the **first** year of follow-up. In case of elevated TSH, free T3 (or total T3) and free T4 are measured. After the first year of follow-up, thyroid function is evaluated only if clinically indicated to continue follow up.

Note: reference point for TSH collection is determined from the last scheduled protocol imaging. The first Follow-up TSH sample must be collected 12 weeks \pm two weeks from the last protocol imaging performed during treatment. If the EOT imaging does not occur in the scheduled imaging interval (every 12 weeks \pm two weeks starting from C1 D1), it should not be utilized to calculate the start of the Follow-up visit and TSH collection. Instead, as a reference, it should be taken into consideration the previous image conducted during the treatment period. In addition, TSH collected at the EOT visit is not considered as the first Follow-up TSH.

- ◆ Record of further anti-cancer treatments;

Note: further anti-cancer therapies should continue to be recorded until withdrawal of consent, death or end of study, which ever occurs first.

- ◆ Survival status (Refer to Section 6.7.4)

- ◆ Assessment of AEs: if a patient is discontinued from study treatment because of an AE considered to be related to study treatment and the event is ongoing 30 days after the last infusion of study treatment, the event must be followed until resolution or determination by the investigator that the event has become stable or irreversible. Serious adverse events will be collected for up to 90 days following discontinuation of treatment or 30 days if the subject initiates new anticancer therapy. Any treatment-related death occurring beyond this time frame must be reported to EORTC.
- ◆ If clinically indicated, the following tests/investigations:

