10.5 Statistical considerations

The key exploratory HRQoL endpoint relevant for this study is the global health/QoL scale. The following sub-scales and single items will be considered as supportive exploratory HRQoL endpoints: pain, fatigue, appetite loss, shortness of breath, cough, chest pain and dyspnea symptom scales. The other available scales will be classified as "other" exploratory analyses; the financial difficulties scale will not be presented.

The global health/QoL scale will be used as primary outcome of interest for this study. A difference of 10 points on the 100-point QLQ-C30 scale either within a patient or between the two arms will be considered as clinically relevant [Ref. 78]. The standard deviation of this scale is approximately 20 points. With the 2-sided alpha set at 5% and a power of 80% to detect a difference of 10 points (effect size of 0.5), a minimum of 128 patients (64 per treatment arm) is required. For an effect size of 0.75 (difference of 15 points), 56 patients (28 per treatment arm) are required. Therefore, this study is sufficiently powered to detect differences in HRQoL.

Data will be scored according to the algorithm described in the EORTC scoring manual. All scales and single items are scored on categorical scales and linearly converted to 0-100 scales.

Changes in HRQoL scores from baseline per time point will be evaluated by classifying them according to the 10 point change threshold into 3 categories: improved/stable/deteriorated. Patients without a valid HRQoL outcome at a certain time will be considered as having deteriorated at that time. For each patient the proportion of assessments spent in a deteriorated state will be calculated and compared between treatment arms using a non-parametric rank order test in the intent-to-treat population of the whole population and in the PD-L1 strong positive subgroup.

In order to assess the robustness of the results, the following sensitivity analyses will be performed:

- ◆ a clinical relevant threshold of 5 and 15 points will be used and patients without a valid HRQoL score will be classified according to the reported reason for non-compliance.
- ◆ If adequate compliance available, patients will be classified on valid HRQoL score received after treatment discontinuation only.
- ◆ The area-under-the-curve (AUC) will be calculated for each patient based on the global health/QoL scores. Missing values will be considered as 0.

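### The HRQoL collection schedule in Section 6.7 and the eligible windows in Section 10.4.1 use different calendars, so forms collected within tolerance after year 1 can fall outside the window

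*Combined protocol and SAP*

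**What the plan says.** Section 10.4.1 lists the windows in which an HRQoL or EQ-5D form is eligible, all counted from randomization. After year 1 these begin with "Can be completed at week 74 (+/-4 weeks) after randomization" and continue with "Can be completed at week 100 (+/-4 weeks) after randomization", "Can be completed at week 152 (+/-4 weeks) after randomization", "Can be completed at week 204 (+/-4 weeks) after randomization" and the same tolerance around week 256. Section 10.4 explains the first of them: "The week 74 assessment therefore corresponds to the last scheduled on-treatment disease assessment visit at week 48 plus 26 weeks", with 26 weeks taken as 6 months.

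The site-facing text is different. Sections 6.7.2.2 and 6.7.3 ask for questionnaires "every 6 months (+/- 4 weeks) during the 2nd year and then yearly (+/- 4 weeks) until year 5", and give no week numbers. Both follow-up sections date their visits from infusion 1: "The reference date for scheduling follow up visits is day 1 of infusion 1". Sections 4.1.3 and 6.3 allow infusion 1 up to 7 days after randomization. Section 10.4 requires forms to be completed at scheduled visits, so visit timing decides which forms fall in a window.

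For scoring, Section 10.5 states: "Patients without a valid HRQoL outcome at a certain time will be considered as having deteriorated at that time".

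**The concern.** The two calendars differ in origin (infusion 1 against randomization). They may also differ in offset, because Section 10.4.1 adds half-years and years to week 48, while a site told to collect six-monthly in year 2 may add them to month 12. A site working within its own tolerance could then complete a form that the analysis calendar does not accept.

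The scoring rule is what gives this weight. Section 10.5 compares, between arms, each patient's proportion of assessments in a deteriorated state. If a completed form rejected on its date leaves the patient without a valid outcome, the time point counts as deterioration whatever the patient answered. This would happen in both arms, so the main effect would be to dilute any real difference, in a trial whose working hypothesis (Section 10.2) is no significant decrement in HRQoL. It would also lower apparent compliance, which Section 10.5.1 uses to decide whether the main analysis goes ahead. EQ-5D shares the windows.

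**Working it through.** **Inputs.** Window centres c = 74, 100, 152, 204 and 256 weeks from randomization, each ±4 weeks (10.4.1). Site tolerance ±4 weeks (6.7.2.2, 6.7.3). Lag from randomization to infusion 1: 0 to 7 days (4.1.3, 6.3). 6 months = 26 weeks (10.4). As an alternative I also convert by calendar: weeks = months × 365.25/12/7.

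**The plan's own figures.** 48 + 26 = 74 and 74 + 26 = 100; then 152, 204 and 256 in steps of 52. The table is reproduced. Section 10.4 says assessments after week 74 come every 26 weeks, whereas the table moves to 52-week steps after week 100.

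**Count A: from week 48, as in 10.4, but dated from infusion 1.** Targets are weeks 74-75, 100-101, 152-153, 204-205 and 256-257 from randomization. Each is at least 3 weeks inside the window end. With a 7-day lag the site window at the first point is 71-79 against 70-78 eligible, so 1 of 8 weeks is lost.

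**Count B: full years from infusion 1 (months 18, 24, 36, 48 and 60).** Target t = months in weeks + lag. Eligible share = overlap of [t − 4, t + 4] with [c − 4, c + 4], divided by 8.

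| Month | Eligible weeks | Target, 26-week rule (lag 0 / 7 days) | Share eligible | Target, calendar (lag 0 / 7 days) | Days past window end | Share eligible |
|---|---|---|---|---|---|---|
| 18 | 70-78 | 78 / 79 | 50% / 38% | 78.3 / 79.3 | 1.9 / 8.9 | 47% / 34% |
| 24 | 96-104 | 104 / 105 | 50% / 38% | 104.4 / 105.4 | 2.5 / 9.5 | 46% / 33% |
| 36 | 148-156 | 156 / 157 | 50% / 38% | 156.5 / 157.5 | 3.7 / 10.7 | 43% / 31% |
| 48 | 200-208 | 208 / 209 | 50% / 38% | 208.7 / 209.7 | 5.0 / 12.0 | 41% / 29% |
| 60 | 252-260 | 260 / 261 | 50% / 38% | 260.9 / 261.9 | 6.2 / 13.2 | 39% / 26% |

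Under the 26-week rule the target is 0 or 7 days past the window end. Example (month 60, calendar, 7-day lag): t = 260.89 + 1 = 261.89; the site window starts at 257.89; the overlap is 260 − 257.89 = 2.11 weeks; 2.11/8 = 26%.

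**Average over the nine post-baseline points.** Assume count B, every form completed, and forms spread evenly over the site window. The four year-1 windows (±3 weeks) are fully covered at lag 0 and 5/6 covered at a 7-day lag. Best case (26-week rule, lag 0): (4 + 5 × 0.50)/9 = 72%. Worst case (calendar, 7-day lag): (4 × 5/6 + 0.34 + 0.33 + 0.31 + 0.29 + 0.26)/9 = 54%.

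**Do the sensitivity analyses protect?** The AUC analysis sets missing values to 0, so a rejected form would get the lowest score. Another analysis reclassifies patients by the reported reason for non-compliance, but under Section 10.4 a reason is recorded only when a form was not filled in. A completed form outside its window has none.

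**The case against.** The strongest reply is that Chapter 10 already says how to count. Section 10.4 derives week 74 from week 48, and note 7 to Table 4 sends sites to Chapter 10. Months 18 to 60 are written nowhere. Under count A the targets sit comfortably inside the windows. This stands, and it is why the larger loss is conditional. It does not remove the problem: the follow-up sections that sites work from give no week numbers, and Section 10.4 is at odds with its own table on the later intervals.

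The origin is also less clear-cut than a plain conflict. The HRQoL notes in 6.7.2.2 and 6.7.3 speak of the first year after randomization, and 6.7.2.2 adds a start at visit 1. The ambiguity is at most 7 days.

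A reader might infer that every on-schedule form after year 1 is invalid, or that a stable patient with punctual forms is counted as deteriorated at five of nine assessments. The documents do not support either. The early part of the site tolerance is always eligible. With infusion 1 on the day of randomization and the plan's 26-week half-year, an on-target form falls on the last day of its window. The inference also needs count B.

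Nor do the documents expressly tie a valid outcome in 10.5 to an eligible window in 10.4.1. That link is the natural reading, since these windows are the only timing criterion given, but it is not written.

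Finally, HRQoL is exploratory and both arms share the schedule. A reader might expect the 50% compliance rule to be triggered. The mismatch alone does not do that: the averages above are 54-72%, and 10.5.1 does not say that compliance is judged by these windows.

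**Conclusion.** The point holds as an unreconciled inconsistency with a conditional effect on the main HRQoL analysis. Under the count in 10.4, the cost is up to 1 week of each window. Under full years from infusion 1, the target is 0 to about 13 days past the end of the eligible window, and about 26-50% of the permitted site window is eligible at five of nine post-baseline time points.

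The scoring consequence rests on reading a valid outcome as one within the 10.4.1 window. The shares assume that forms are spread evenly over the site tolerance. The lower end also assumes calendar months and the full 7-day lag for every patient. The form schedule on the data-capture website and in the completion guidelines (15.1) is not in these documents, so which count sites follow cannot be settled here. The primary and secondary efficacy endpoints are not affected.

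**What to change.** Before unblinding:

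- Use one anchor in 6.7 and 10.4.1: day 1 of infusion 1, or randomization for a patient never dosed.
- Print one set of nominal weeks in both places, and correct the interval sentence in 10.4 to match.
- Make the eligible windows cover every form collected within the 6.7.2.2/6.7.3 tolerance under either count. For example, with the anchor moved to infusion 1, extend the upper limits of the five late windows by 5 weeks, giving 70-83, 96-109, 148-161, 200-213 and 252-265. The latest in-tolerance dates under calendar counting are 82.3, 108.4, 160.5, 212.7 and 264.9, so all are covered and no windows overlap.
- State in 10.5 that a completed form within these windows is valid, and that a completed form is not scored as deteriorated solely because of its date. Apply the same rule to the AUC analysis, to compliance, and to forms already collected.

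The cost is protocol and SAP wording plus one derivation rule, with no added visits or forms. Fixing it while still blinded avoids a data-dependent choice of windows.
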